10.1 SAMPLE SIZE JUSTIFICATION

This study will enroll a minimum of 140 subjects who will receive office-based CTR-US. This sample size provides adequate statistical power for the evaluation of the primary endpoint given the assumptions below:

- Primary endpoint: BCTQ-SSS change at 3 months
- Statistical test: Linear mixed model
- Two-tailed alpha: 0.05
- Standard deviation change in BCTQ-SSS at 3 months: 0.75 points
- Subject attrition: 15%

The results of this power analysis show that a sample size of 100 evaluable subjects provides 90% statistical power to detect a mean change of 0.2 points on the BCTQ-SSS at 3 months. To account for reasonable subject attrition, a minimum of 140 subjects will be enrolled in the trial.

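### In 10.1 the figures 100 evaluable, 15% attrition and 140 enrolled do not come from one calculation; the gap errs on the safe side, but the expected evaluable number and the power sentence need restating

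*Combined protocol and SAP*

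**What the plan says.** All the relevant figures are in section 10.1 (Sample Size Justification):

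- Enrolment: "This study will enroll a minimum of 140 subjects who will receive office-based CTR-US".
- Assumed loss: "Subject attrition: 15" percent.
- Evaluable number and power: "a sample size of 100 evaluable subjects provides 90% statistical power to detect a mean change of 0.2 points on the BCTQ-SSS at 3 months".
- Test settings: "Two-tailed alpha: 0.05" and "Standard deviation change in BCTQ-SSS at 3 months: 0.75 points", with a linear mixed model as the test.
- Reason for the step from 100 to 140: "To account for reasonable subject attrition, a minimum of 140 subjects will be enrolled in the trial".

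No other allowance appears in 10.1. Section 7 counts a subject as enrolled only once CTR-US has been received, so the 140 are treated subjects. Section 10.2 limits the primary analysis to treated subjects who meet all eligibility criteria. Section 10.2.3 plans no imputation and reports the primary endpoint as a mean change with a 95% confidence interval.

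**The concern.** A reader of 10.1 expects 140 to be 100 inflated for 15% attrition, because attrition is the only stated reason for the increase and 15% is the only stated rate. It is not. Two things are then unclear.

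The first is the planned evaluable number. It could be 100, the number the power sentence uses, or 119, the number that 140 and 15% imply. The single power statement in the plan depends on which is meant.

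The second is the tolerable loss. At 15% the trial loses 21 of 140 subjects; the distance from 140 to 100 is 40. Anyone following retention against the plan cannot tell which figure marks a departure from it.

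**Working it through.** **Inputs, all from 10.1:** 100 evaluable; 15% attrition; 140 enrolled; change to detect 0.2 points; SD of the change 0.75; two-sided alpha 0.05; stated power 90%.

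**Attempt to reproduce 140.**
- Correct inflation, n/(1 - d): 100/0.85 = 117.6, so 118.
- Common shortcut, n x (1 + d): 100 x 1.15 = 115.
- Neither gives 140. The excess over the correct figure is 140 - 118 = 22 subjects, or 22/118 = 19%.

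**Reverse check.**
- 140 x (1 - 0.15) = 119 evaluable.
- Attrition that takes 140 to 100: 1 - 100/140 = 28.6%, nearly twice the listed rate.

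**Power at each candidate evaluable number.** The mixed model is approximated by a one-sample test of the mean change with one observation per subject: power = Phi(0.2 x sqrt(n)/0.75 - 1.960). The change detectable with 90% power is (1.960 + 1.282) x 0.75/sqrt(n).

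| Evaluable n | 0.2 x sqrt(n)/0.75 | Power, normal (t) | Detectable at 90% |
|---|---|---|---|
| 100 | 2.667 | 76.0% (75.2%) | 0.243 |
| 119 | 2.909 | 82.9% (82.3%) | 0.223 |

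The stated 90% for 0.2 points is therefore reproduced at neither number. It needs ((1.960 + 1.282) x 0.75/0.2)^2 = 147.8, so 148 evaluable (150 with the t distribution).

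**Precision, for scale.** The 95% half-width, 1.96 x 0.75/sqrt(n), is 0.147 points at 100 and 0.135 at 119, a difference of 0.012 on a scale from 1 to 5.

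**Sensitivity to bilateral procedures.** BCTQ-SSS is measured on every treated hand (7.2.2), so a subject treated bilaterally adds information. The plan states neither the bilateral share nor the within-subject correlation. The ranges here are assumptions: a share b from 14.5% (the registry's simultaneous cases, section 5) to 50%, a correlation r from 0.3 to 0.7, and 0.75 taken as the per-hand SD. The effective number is n x ((1 - b) + 2b/(1 + r)).
- n = 100: effective 102.6 to 126.9, power 77% to 85%.
- n = 119: effective 122.0 to 151.0, power 84% to 91%.

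Only the most favourable corner (half the subjects bilateral, r = 0.3, 119 evaluable) reaches 90%. None of this bears on the attrition step, which counts subjects.

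**Near-misses for 140.** Applying 15% twice gives 100/0.85^2 = 138.4, so 139, but no second loss is described. A one-sided 0.05 test needs 121 evaluable, hence 121/0.85 = 142.4, so 143 enrolled, but the plan states a two-tailed alpha. Both are conjecture.

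**The case against.** The strongest reply is that nothing goes wrong in the trial. The target is a floor, it exceeds the 118 that 15% attrition requires, and 10.1 never says in so many words that 140 less 15% equals 100. It says that 100 gives the stated power and that at least 140 will be enrolled. A margin is also sensible on the documents' own evidence. The registry in section 5 had 3-month data on 446 of 535 patients (89/535 = 16.6% lost). Section 7.3.2.1 withdraws subjects who have further surgery on either hand within 3 months. Section 10.2 drops treated subjects found ineligible.

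Most of this stands. A reader might infer from the mismatch that the trial is too small or that its success test is at risk; the documents do not support that. On attrition alone the error is on the safe side. Success in 10.2.3 needs only a 3-month mean significantly below baseline, and section 5 reports earlier 3-month falls of about 1.5 points (3.0 to 1.5) and 1.6 points, far above 0.2.

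A reader might also infer that the sponsor really expects 28.6% loss. The documents do not say so. The registry's 6-month loss (162/535 = 30.3%) is close to that figure, but the primary endpoint is at 3 months, where the loss was near the listed 15%.

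What does not stand is the idea that the margin explains itself. Attrition is the only reason 10.1 gives, and none of the other losses is mentioned there. Pre-treatment dropout cannot account for the gap, because under section 7 the 140 have already been treated. Nor can bilateral procedures, since a second hand adds information and does not call for more subjects.

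**Conclusion.** The point holds as an internal inconsistency in the plan's only sample-size justification. With 15% attrition, 100 evaluable subjects need 118 enrolled, and 140 enrolled leave 119; the pair 140 and 100 implies 28.6%. This arithmetic needs no assumption beyond the plan's own figures.

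The consequence is limited to documentation. No enrolment number, analysis or success decision changes. It would overstate the matter to say that precision claims in the plan are undermined, because 10.1 contains no precision statement.

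The inconsistency cannot be tidied in isolation, because the power sentence beside it is not supported at either candidate number: about 76% at 100 and about 83% at 119 for a 0.2-point change. Those percentages rest on SD 0.75, two-sided 0.05 and roughly one observation per subject. Bilateral data would raise them by an amount the plan does not quantify.

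**What to change.** In 10.1, keep 140 enrolled and 15% attrition, and state that 119 evaluable subjects are expected at 3 months. Restate the power sentence on 119: about 83% power to detect a 0.2-point change, or 90% power to detect about 0.22 points, at SD 0.75 and two-sided 0.05, labelled as approximating one observation per subject. If credit is to be taken for bilateral procedures, give the assumed share and within-subject correlation.

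If the 22 subjects above 118 are a deliberate margin, for example for ineligible treated subjects or withdrawals after further surgery, say so and name the reason.

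Two shortcuts should be avoided. Raising attrition to 28.6% so that 140 returns 100 would fit the rate backwards to the answer and leave the power claim uncorrected. Carrying over 90% power for 0.2 points with either 100 or 119 would repeat a figure that the stated inputs do not give.

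The cost is a short rewording of 10.1, with no change to enrolment, procedures or analysis.

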10.2 ANALYSIS POPULATIONS

The primary statistical analyses will be performed on subjects who meet all study eligibility criteria and receive treatment with CTR-US. Subjects who withdraw from the study prior to treatment will not be included in the analysis.

10.2.1 Duration Variables

Study day 0 is the day the subject receives office-based CTR-US. Postoperative study day will be calculated relative to day 0 as follows:

Study Day = (Date of Event – Date of Treatment)

10.2.2 Analysis Windows

Study data will be categorized into discrete, contiguous reporting windows to ensure that all available data are included in the analyses. The analysis windows for this study are defined below:

Study Visit	Target Days	Analysis Window
Treatment	0	0
2 weeks	14	7-22
1 month	30	23-60
3 months	90	61-135
6 months	180	136-270
12 months	365	271-547
24 months	730	548-912

10.2.3 Data Analysis Methods

Baseline data will be analyzed using descriptive statistics. Continuous data will be summarized using mean and standard deviation for normally distributed data, median and interquartile range for non-normally distributed data, and counts and percentages for categorical data. For categorical variables, percentages will be calculated based on non-missing data.

The primary endpoint will be reported as the mean change in BCTQ-SSS at 3 months relative to baseline. Data will be reported as the mean change and 95% confidence interval. A linear mixed model will be the statistical test used to assess the primary endpoint, which accounts for the correlation inherent with bilateral procedures ⁴¹. The study will be deemed successful if the mean BCTQ-SSS score at 3 months is statistically significantly lower than at baseline, as determined by a p-value less than 0.05 using the linear mixed model.

Time to return to normal daily activities and time to return to work among employed individuals will be reported as the median and interquartile range in each treatment group.

Longitudinally measured continuous outcomes (i.e., BCTQ-SSS, BCTQ-FSS, MHQ, Numeric Pain Scale, EQ-5D-5L) will be analyzed using a linear mixed model.

Adverse events will be reported using counts, percentages and exact 95% confidence intervals using Clopper-Pearson's method. Calculation of AE incidence will be performed on a persubject basis.

Statistical analyses will be performed using a two-sided hypothesis test at a 5% level of significance. No adjustments for multiplicity are planned. Missing data imputation will not be performed. Subgroup analyses will be performed for subjects undergoing a unilateral or bilateral simultaneous procedure.

11.STUDY RESPONSIBILITIES AND MANAGEMENT

This study will be performed in accordance with all requirements set forth in the U.S. regulations, 21 Code of Federal Regulations (CFR) Parts 812, 50, 54, and 56, the Declaration of Helsinki, and any other applicable local laws, regulations, or guidelines.

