7.2.4 Loss to Follow-up

If a subject fails to comply with follow-up evaluations, the investigational site must make at least two repeated attempts to contact the subject. Each attempt to contact the subject and the method used (e.g., telephone contact, registered letter) must be documented in the subject's records.

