7.3 SUBJECT WITHDRAWAL FROM STUDY

7.3.1 Voluntary Withdrawal

A subject may voluntarily withdraw from the study at any time. If a subject officially withdraws from the study, the investigator must ensure that the reason for the withdrawal is documented. If the subject had an AE, the subject should be followed until the resolution of the AE, if possible. Data from these subjects will be included in the analysis up to the point of each subject's withdrawal.

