7.3.2 Involuntary Withdrawal

A subject also may be withdrawn by the investigator if the investigator determines that continued subject participation in the study will have a negative effect on the safety of the subject. Data obtained up to the date of subject withdrawal will be included in the study.

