8.2 SECONDARY ENDPOINTS

8.2.1 Time to Return to Normal Daily Activities

Time to return to normal daily activities will be ascertained through the ViedocMe ePRO module which asks whether the subject has returned to normal daily activities outside of work. Reminders will be sent to the subjects either by email or text messaging to minimize the risk of missing data. Time to return to normal daily activities postoperatively will represent a secondary endpoint of the study. The time to return to normal daily activities will be defined as the number of days between treatment and the time the subject reports returning to normal daily activities, irrespective of work status.

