8.2.2 Time to Return to Work Among Employed Subjects

Among study subjects who report full-time or part-time employment, time to return to work will be ascertained through the ViedocMe ePRO module by asking whether the subject has returned to work in any capacity (full or limited). Reminders will be sent to the subjects either by email or text messaging to minimize the risk of missing data. Time to return to work postoperatively will represent a secondary endpoint of the study. The time to return to work will be defined as the number of days between treatment and the time the subject reports returning to work in any capacity.

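### Times to return to activities and to work have no censoring rule, so a subject lost before reporting a return drops out of the summary; the effect is small and the fix is cheap

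*Combined protocol and SAP*

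**What the plan says.** Both endpoints are times to an event. Section 8.2.2 defines the work endpoint as "the number of days between treatment and the time the subject reports returning to work in any capacity", and section 8.2.1 defines the activities endpoint in the same way. Section 10.2.3 plans one summary for both: they "will be reported as the median and interquartile range in each treatment group". The trial has a single arm, so the only groups this could mean are the unilateral and simultaneous bilateral subgroups named later in the same section.

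For incomplete data, section 10.2.3 adds: "Missing data imputation will not be performed". Section 7.3.1 says of voluntary withdrawals: "Data from these subjects will be included in the analysis up to the point of each" subject's withdrawal. Section 7.3.2 says of involuntary withdrawals: "Data obtained up to the date of subject withdrawal will be included in the study". Two measures aim to limit loss: reminders (section 8.2.1: "Reminders will be sent to the subjects either by email or text messaging to minimize the risk of missing data") and, under section 7.2.4, "the investigational site must make at least two repeated attempts to contact the subject".

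The plan does not mention censoring, Kaplan-Meier estimation, ranking non-returners last, or a count of subjects without a return time.

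**The concern.** A subject who leaves on day 10 and is not yet back at work tells us that the return time exceeds 10 days. A plain median of observed times cannot use that. With no value defined and no imputation, the natural default is to omit the subject.

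Omission is not neutral even when loss has nothing to do with recovery. Slower subjects have longer in which to be lost, so the observed times lean short. If loss does depend on recovery, the error may go in either direction.

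These are the first two secondary endpoints in the synopsis. Section 3 presents recovery time as relevant to shared decision-making, and section 9.8.2 lists rapid return as a possible benefit. With no comparator, any error sits directly in the reported figure. Without a rule, the choice between omitting, censoring and ranking last could be made after the data are seen.

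**Working it through.** The plan gives no sample size or precision for these endpoints, so there is no figure of its own to reproduce. The question is how much omission could matter.

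**Inputs (section 5, registry; applying them to this trial is an assumption)**
- Work: median 5 days, IQR 3 to 9, 92.3% back by 2 weeks.
- Activities: median 3 days, IQR 2 to 5, 96.5% back by 2 weeks.
- Follow-up available: 93% at 2 weeks, 89% at 1 month, 83% at 3 months. Loss is taken as 7%, 11% and 17%, linear between these points.
- Employed share 62%: 0.62 × 140 = 87 subjects.

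**Three shapes for the work times**
- A: straight lines through the registry points, then to day 30.
- B: log-normal, median 5, upper quartile 9; sigma = ln(9/5)/0.6745 = 0.871.
- C: log-normal, median 5, 92.3% by day 14; sigma = ln(14/5)/z(0.923) = 0.722, upper quartile 8.14.

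Activities use the same three forms with the activities figures.

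**Loss unrelated to recovery.** Let G(t) be the share still responding at day t and f(t) the density of return times. The share without a time is 1 − ∫f(t)G(t)dt, and the observed times have density proportional to f(t)G(t).

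| Work | A | B | C |
|---|---|---|---|
| Share without a time | 3.3% | 3.3% | 3.1% |
| Median, omitted (true 5) | 4.92 | 4.89 | 4.93 |
| Upper quartile, omitted | 8.85 | 8.76 | 7.99 |
| True upper quartile | 9 | 9 | 8.14 |
| Upper quartile shortfall | 0.15 | 0.24 | 0.15 |

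That is about 3 of 87 employed subjects. For activities, 2.0% to 2.3% (3 of 140) have no time; the median is 0.03 to 0.04 day short and the upper quartile 0.06 to 0.09 day short. Kaplan-Meier with censoring returns the true values under this kind of loss (work median 5.00; upper quartile 9.00, 9.00 and 8.13 by simulation).

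**Slowest 7% lost** (0.07 × 87 = 6 employed; 0.07 × 140 = 10 overall). The reported q-quantile is the true 0.93q quantile, so the median is the true 46.5th percentile and the upper quartile the true 69.75th.
- Work median (A/B/C): 4.72, 4.63, 4.69.
- Work upper quartile: 8.16, 7.85, 7.26.
- Activities median: 2.86, 2.81, 2.78.

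**Fastest 7% lost at the start.** The reported q-quantile is the true (0.07 + 0.93q) quantile, so the median is the true 53.5th percentile.
- Work median: 5.56, 5.40, 5.33. Kaplan-Meier gives the same.
- Counting these subjects as not returned makes the reported median the true 57th percentile: 6.12, 5.83, 5.68.

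**Outer limit.** If the whole 15% attrition in section 10.1 were the slowest returners, the reported median would be the true 42.5th percentile. The work median would be 4.2 to 4.4 and its upper quartile 6.4 to 7.2.

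**Against sampling error (model B).** SE = √(q(1−q)/n)/f, where f is the density at that quantile. For work with n = 87, the SE is 0.59 day at the median and 1.15 days at the upper quartile. For the activities median with n = 140 it is 0.24 day. The work-median shift of about 0.1 day under unrelated loss is less than one fifth of its SE (0.11/0.59 = 0.19).

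**The case against.** The strongest reply is that this hardly matters. The likely shift is far below sampling error. Under unrelated loss, or loss of the slowest 7%, times rounded up to whole days still give medians of 5 and 3. The endpoints are descriptive. The 7% figure is also only a proxy: it is questionnaire availability at 2 weeks, and this trial asks about return daily to day 14 and again at 1 and 3 months, so a missing form is not the same as loss before return. All of that stands, and it sets the low severity.

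Four stronger readings are tempting, but the documents do not support them.

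- *The reported times will be too favourable.* This holds if loss is unrelated to recovery or falls on slow subjects. Subjects who feel well may equally stop answering, and the documents favour neither pattern. If the ePRO records only yes or no (the form is not shown), a missed daily answer also delays the recorded return. With 90% of daily answers given (assumed), that is about 0.13 to 0.15 day the other way under model B.
- *The plan contradicts itself.* Sections 7.3.1 and 7.3.2 are satisfied when a return reported before withdrawal is used. The aim in section 10.2.2, "to ensure that all available data are included in the analyses", concerns visit windows. Neither conflicts with section 10.2.3; they simply do not settle the censoring question.
- *The number omitted will go unreported.* The plan is silent on this. Section 7.3.3 requires an End of Study form for subjects lost to follow-up, so their status is recorded.
- *Kaplan-Meier and a not-returned analysis would bracket the truth.* They do not when the fastest are lost: both then exceed the true work median of 5.

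What remains is that reminders and contact attempts reduce loss but do not say how to analyse subjects who are still lost.

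**Conclusion.** The point holds as a low-severity improvement. The definitions, the plain median and IQR, and the bar on imputation together leave a subject lost before reporting without a value, and no analysis rule covers that case. A better method than the stated one is available at almost no cost.

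If loss is unrelated to recovery, the reported times are slightly short. If loss depends on recovery, the direction is unknown. In the fastest-lost extreme a work median rounded up to whole days would print as 6 rather than 5; otherwise the whole-day medians would probably not change. The primary endpoint and the success rule are unaffected.

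The sizes rest on registry recovery times and loss, on assumed distribution shapes, and on the registry's employed share. The registry times themselves come from the 373 of 535 patients (70%) with 6-month follow-up.

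**What to change.** In section 10.2.3, replace the sentence on the two time endpoints with:

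*Kaplan-Meier median and quartiles with 95% CIs will be reported overall and by unilateral or simultaneous bilateral procedure. Subjects who have not reported a return are censored at their last response, and the number censored will be given.*

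This also removes the reference to treatment groups in a single-arm trial.

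Optional additions:
- A sensitivity analysis counting lost subjects as not returned. Kaplan-Meier does not remove bias when loss depends on recovery, so this shows one extreme. It should be described as that, not as a bound, and named as an exception to the no-imputation rule.
- A statement in sections 8.2.1 and 8.2.2 that the date of return follows section 10.2.1 (event date less treatment date). If the ePRO holds only yes/no answers, an interval-censored estimator such as Turnbull's is an option.

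The cost is a few sentences and slightly more analysis, with no extra visits, subjects or required data. The reported times may come out slightly less favourable.

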11.1 INVESTIGATOR RESPONSIBILITIES

Each investigator will be responsible for ensuring the investigation is conducted according to all signed agreements, the study protocol, IRB requirements, and applicable laws and regulations. Investigators may not begin enrollment until the Sponsor, or its designee, receives and approves (when necessary) the following documents:

- · Signed Investigator Agreement
- Financial disclosure forms for all participating investigators
- · IRB roster (or IRB registration number from the Office of Human Research Protection)
- · IRB protocol and ICF approvals
- · Investigators' current curricula vitae and medical license
- Signed Site Delegation Log

It is acceptable for Investigators to delegate one or more of the above functions to a Co- or Sub-Investigator, or a trained Research Coordinator; however, the Investigator remains responsible for the proper conduct of the clinical investigation, including obtaining and documenting proper study informed consent, collecting all required data, submitting accurate and complete CRFs, etc.

At each study site, appropriate procedures must be followed to maintain subject confidentiality according to appropriate local regulations (e.g., Health Insurance Portability and Accountability Act (HIPAA) in the U.S.). Each site may have its own internal procedures or requirements for use and release of subject medical information in research studies. Each Investigator is responsible for obtaining appropriate approvals, consents, or releases of medical information as dictated by their relevant subject privacy laws.

The study is not transferable to other sites attended by the Investigator unless prior approval is obtained from the appropriate IRB and the Sponsor.

